1.3 Study Objectives

Primary objective:

To assess both safety and patient and clinical acceptance of the LumenEye device with specialist consultation over the CHiP platform.

Secondary objectives:

1. To establish the clinical utility of the CHiP software system for performing remote telemedicine assessment of the rectum and colon.
2. To provide pilot data for the diagnostic accuracy of the LumenEye system for colitis severity, cancer, rectal polyps and benign disease of the rectum and anus.

2 Study Design

We propose a multi-centre prospective observational pilot study of the LumenEye and CHiP system. The experimental design is pragmatic and designed to permit the recruitment of patients in a timely fashion necessary for a prospective, confirmatory analysis during the Covid-19 pandemic. The study outline is provided in figure 3.

[figure not shown]

Figure 3. Overview of study protocol

2.1 Recruitment

Patients will be identified for recruitment via two routes:

1. Patients with an established diagnosis of inflammatory bowel disease who have been identified as being 'at risk' by either their secondary care doctor or GP and now require endoscopic assessment for ongoing disease symptoms but are unable to access endoscopy services urgently.
2. Patients presenting directly to their GP practice with symptoms of anorectal disease (e.g. rectal bleeding or pain) or symptoms that would warrant referral to a hospital under a 2WW appointment according to NICE criteria

All patients will be provided with written information about the study and an online website will be created to provide this information. The study aims to recruit 100 patients into the pilot study.

2.2 Quality assurance and training

All clinicians will be provided with an onboarding protocol and a LumenEye SOP for standardised use, which include recommendations for use during the Covid-19 pandemic will be created. All clinicians performing investigations with the LumenEye will undergo training and quality assurance assessment. The first 5 procedures will be performed with a proctor to ensure that this is performed safely using appropriate PPE according to Public Health England Recommendations.

The primary study site will be based at Imperial College NHS trust which is a recognized National Bowel Cancer Screening (NBCS) Centre of excellence. The Imperial endoscopy suite performs over 10,000 endoscopic procedures each year. Additional primary sites will be located at:

King's College Hospital NHS Foundation Trust- [name]
NHS Frimley Health Foundation Trust – [name]

All patients enrolled into the study will be asked to have either an enema or glycerine suppository prior to the examination. They will be examined by the primary care physician in the clinic as per a standard rigid sigmoidoscopy assessment. Physicians may take biopsies if required but only if the physician feels this is warranted for clinical use. There is no requirement for research specimens in this study.

All doctors using the LumenEye will be asked to record images showing standard anatomical locations including:

1. The rectosigmoid junction
2. Each rectal haustral fold
3. Exit from the rectum.

Videos will also be recorded for any pathology identified.

Virtual clinics will be coordinated by the CI and Co-Is. During these clinics, a secondary care physician or surgeon will be available to discuss the case with the GP. These could be performed in real time with the patient present during a live examination or they could be performed retrospectively as part of a multidisciplinary team meeting.

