1.1.4 LumenEye and CHiP

The intervention: The LumenEye X1 (SurgEase Innovations Ltd, UK) is a CE Marked novel point of care rigid digital endoscope which provides High-Definition views of the rectum up to 20cm from the anal verge. It permits endoscopic biopsy under view (figure 1) and maintains pneumorectum sufficiently with as little as 100ml of air. Air delivery is in a closed system thereby significantly reducing aerosol transmission relative to formal endoscopy. This feature is particularly attractive in the current Covid-19 pandemic. A removable disposable manifold and a chemical clean with Tristel™ Trio is the only requirement for reprocessing

which is more cost-effective than automated washing & sterilisation. All images and videos are displayed on a HD screen, supplied alongside the scope, which can be captured and stored securely on the cloud platform (called CHiP, Figure 2) which allows retrospective review of images and data taken during rectoscopy from any device. The technology permits high quality endoscopy at the bedside and outside of traditional tiers of care which is particularly attractive during the current Corona pandemic. An additional feature of CHiP includes telemedicine functionality with live video sharing of the camera feed; a proctor can be invited over WIFI into a session who can then view the live feed from the scope and offer advice and guidance. The technology can offer cost-effective, immediate tumour visualisation, critical measurement, opportunity for biopsy and virtual diagnostic support.

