2.3 Analysis

Clinicians will be asked to provide qualitative feedback data with each use concerning device performance. This will be in the form of a short questionnaire, split into technical performance, views achieved, diagnostic yield, quality of the telemedicine interaction, patient outcome (discharged or referred to formal endoscopy) and adverse events.

Local users of the LumenEye system will undergo nasal swab assessments every 4 weeks for a covid-19 PCR test to ensure staff safety is maintained during the study. If a swab tests positive, the physician will be asked to follow standard PHE advice on isolation, contact tracing and further treatment.

All LumenEye devices will undergo at least one random post-cleaning swab test for Covid-19 to confirm the Tristel Trio cleaning system sufficiently eradicates SARS-COV-2 from the LumenEye. (An analysis of this has been performed outside of the study which confirms the efficacy of the Tristel Trio system against SARS-COV-2).

Patient feedback will be requested through a validated questionnaire..

All clinicians providing advice and guidance via CHiP will be asked to provide data on the quality of the views, the stability of the platform and to provide information on the diagnosis. For flare patients, both clinicians will be asked to report Mayo flare scores based on observed

data. For adenomas, clinicians will be asked to report anatomical location, morphology, and Paris endoscopy assessment scores. All data pertaining to follow up colonoscopy or flexible sigmoidoscopy will be used as a comparator group for a diagnostic sensitivity / specificity analysis.

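### Specialist CHiP readings may be made after the follow-up endoscopy result is known; if those readings serve as the LumenEye result, its apparent accuracy can be inflated

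*Combined protocol and SAP*

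**What the plan says.** Under section 2.2, the primary care physician examines the patient with the LumenEye, and a secondary care physician or surgeon discusses the case in a virtual clinic. That discussion may be live, or "they could be performed retrospectively as part of a multidisciplinary team meeting". Section 1.1.4, which is background, describes the stored-image feature that makes this possible: CHiP "allows retrospective review of images and data taken during rectoscopy from any device".

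Section 2.3 sets out what is collected:

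- CHiP advisers report view quality and platform stability, and are asked "to provide information on the diagnosis".
- For flare patients, "both clinicians will be asked to report Mayo flare scores", resting on what was observed.
- For adenomas, "clinicians will be asked to report anatomical location, morphology, and Paris endoscopy assessment scores". This request is not limited to the adviser.

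The same paragraph ends with the accuracy analysis: follow-up colonoscopy or flexible sigmoidoscopy data "will be used as a comparator group for a diagnostic sensitivity / specificity analysis".

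Section 6 says that the data will inform a power calculation for later studies and that standard univariate methods will be used. Neither section 2.3 nor section 6 states whose reading is the index test, when it must be recorded, or whether the reader is masked to the follow-up result.

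**The concern.** An accuracy estimate needs an index reading made without knowledge of the comparator. Here the person asked for a diagnosis may give it at a meeting with no latest date. By then the follow-up endoscopy report may be in the file, and so may histology from a biopsy allowed by section 2.2. The adviser works in secondary care, and nothing in the text prevents the adviser from having performed that endoscopy. A miss on the LumenEye images can then be corrected towards the comparator and be scored as a correct LumenEye reading.

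At stake is secondary objective 2 (section 1.3), the pilot accuracy data. Sensitivity, specificity and any agreement of Mayo or Paris scores with follow-up endoscopy would tend to move upwards, and a later study planned on these figures could be too small. The problem cannot be repaired at analysis, because the text does not require the timing of each reading, or what the reader already knew, to be recorded.

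**Working it through.** The plan gives no figure to reproduce. The target of 100 patients (section 2.1) has no precision or power statement behind it. The check therefore reads the sections together and then puts an illustrative size on the effect.

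**Step 1. Is the order fixed?** Section 2.2 allows review after the LumenEye examination. Section 2.3 defines the comparator by follow-up endoscopy. No text places one before the other, and no text sets masking, a time limit or a lock on the reading. The nearest safeguard is that Mayo scores should rest on what was observed. It covers flare patients only, and it describes the basis of the score without withholding the result.

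**Step 2. When does the bias enter?** It depends on which reading is the index test, which the protocol leaves open.

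| Index reading | Effect of a late specialist review |
|---|---|
| Local clinician, recorded at the examination | None by this route |
| Specialist | Possible |
| Consensus using the specialist's view | Possible |

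**Step 3. How large could it be?** Let s be true sensitivity, r the share of would-be missed cases read with the endoscopy result known, and c the share of those changed to agree with it. Correct readings already agree with the comparator and stay as they are. Then

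apparent sensitivity = s + (1 − s) × r × c, and the inflation is (1 − s) × r × c.

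All three inputs are assumptions; the documents give none of them.

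| s | r | c | Apparent sensitivity | Inflation (points) |
|---|---|---|---|---|
| any | 0 | any | s | 0 |
| 0.70 | 0.25 | 0.25 | 0.70 + 0.30 × 0.0625 = 0.719 | 1.9 |
| 0.80 | 0.5 | 0.25 | 0.80 + 0.20 × 0.125 = 0.825 | 2.5 |
| 0.75 | 0.2 | 0.8 | 0.75 + 0.25 × 0.16 = 0.79 | 4 |
| 0.80 | 0.5 | 0.5 | 0.80 + 0.20 × 0.25 = 0.85 | 5 |
| 0.75 | 0.5 | 0.8 | 0.75 + 0.25 × 0.40 = 0.85 | 10 |
| 0.75 | 0.8 | 0.8 | 0.75 + 0.25 × 0.64 = 0.91 | 16 |

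The rows with r above zero span about 2 to 16 points. This is not a bound. With s = 0.90 and r = c = 0.25 the inflation is 0.10 × 0.0625 = 0.6 points. With r = c = 1 it reaches its ceiling of 1 − s, which is 20 points at s = 0.80. The same algebra applies to specificity, with false positives in place of misses. No size is calculated for score agreement.

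**Step 4. Against sampling error.** If, as an assumption, 20 diseased patients had follow-up and 16 were detected, the exact 95% interval for sensitivity would be 56% to 94%. A bias of a few points would not be visible in such data.

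**The case against.** The strongest reply is that the specialist's reading may not be the index test at all. The local physician performs the examination, and section 2.3 asks for a questionnaire with each use that covers diagnostic yield. If that reading is the one analysed, the problem does not arise by this route. This stands as a condition on the point. It does not remove it, because the specialist's diagnosis is requested in the very paragraph that defines the accuracy analysis, and nothing excludes it.

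Second, in section 2.2 retrospective is the opposite of live with the patient present. It means after the LumenEye examination, not after endoscopy. The setting suggests that review would often come first: the advice bears on whether the patient is referred, one recruitment route is for patients without urgent access to endoscopy (section 2.1), and endoscopy services were largely halted (section 1.1.3). This too stands. Contaminated readings are possible, but the documents do not show that they are common.

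Third, accuracy is a secondary pilot objective in a feasibility study and will be imprecise anyway. That limits the weight of the point. However, more patients would not reduce this bias, and section 6 intends the estimate for planning later work.

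The study outline in Figure 3 is not shown in the text available, and the device SOP mentioned in section 2.2 is not part of it. Either might bear on timing.

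**Conclusion.** The point holds in conditional form. The text permits specialist readings made with the follow-up endoscopy result known, and if such readings form the LumenEye result, alone or through a consensus, apparent accuracy and agreement can be inflated. The size cannot be derived from the documents: zero if all reviews precede endoscopy, and about 2 to 16 points of sensitivity in the intermediate scenarios above, whose inputs are all assumed. The primary outcome of safety and acceptance is untouched.

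Three stronger readings are not supported:

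- A reader might infer that the accuracy results will be inflated. The documents fix neither the order of events nor the index reading, so they show only that inflation can occur.
- A reader might treat histology as part of the comparator. Section 2.3 names only colonoscopy and flexible sigmoidoscopy; biopsy histology is a further source of unmasked information.
- A reader might take 91% as the expected apparent sensitivity. It is one scenario, with four in five of the would-be misses read late and most of those corrected.

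**What to change.** In sections 2.2 and 2.3:

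1. Name the index reading for the accuracy analysis: local, specialist or a defined consensus.
2. Require the local and the specialist diagnosis and scores to be entered and time-stamped before that reader sees the follow-up endoscopy report or any biopsy histology.
3. Record for each reading whether it was live or retrospective, whether the follow-up result was already known, and whether the reader performed the follow-up endoscopy.
4. Base the main sensitivity, specificity and agreement estimates on readings made without the result, and report the other readings separately.

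Team-meeting review for patient care continues unchanged.

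The cost is a short addition to the form and fewer readings in the main accuracy estimate. How many are lost depends on how many reviews are late: if few, both the loss and the bias are small; if many, the loss is substantial. If harder cases tend to go to team meetings, the main estimate would also come from a somewhat easier set. Reporting the informed readings alongside, instead of discarding them, lets the reader judge this. Recording whether the reader was also the follow-up endoscopist avoids imposing a staffing rule on the sites.

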2.3 Analysis

Clinicians will be asked to provide qualitative feedback data with each use concerning device performance. This will be in the form of a short questionnaire, split into technical performance, views achieved, diagnostic yield, quality of the telemedicine interaction, patient outcome (discharged or referred to formal endoscopy) and adverse events.

Local users of the LumenEye system will undergo nasal swab assessments every 4 weeks for a covid-19 PCR test to ensure staff safety is maintained during the study. If a swab tests positive, the physician will be asked to follow standard PHE advice on isolation, contact tracing and further treatment.

All LumenEye devices will undergo at least one random post-cleaning swab test for Covid-19 to confirm the Tristel Trio cleaning system sufficiently eradicates SARS-COV-2 from the LumenEye. (An analysis of this has been performed outside of the study which confirms the efficacy of the Tristel Trio system against SARS-COV-2).

Patient feedback will be requested through a validated questionnaire..

All clinicians providing advice and guidance via CHiP will be asked to provide data on the quality of the views, the stability of the platform and to provide information on the diagnosis. For flare patients, both clinicians will be asked to report Mayo flare scores based on observed

data. For adenomas, clinicians will be asked to report anatomical location, morphology, and Paris endoscopy assessment scores. All data pertaining to follow up colonoscopy or flexible sigmoidoscopy will be used as a comparator group for a diagnostic sensitivity / specificity analysis.

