1.2 Rationale for current study

The LumenEye scope and CHiP platform will be piloted in a number of clinical settings including remote colorectal clinics. The rationale is to perform an initial pilot study to determine the clinical utility of the LumenEye device for use in primary and secondary care settings. The main hypothesis is that digital rectoscopy is safe and acceptable to clinicians including general practitioners and can significantly reduce the burden of endoscopy referral to and within secondary care centres.

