2.4 Study Outcome Measures

Primary outcome:

Both safety and patient and clinical acceptance of the LumenEye device with specialist consultation over the CHiP platform.

Secondary outcomes:

1. To establish the clinical utility of the CHiP software system for performing remote telemedicine assessment of the rectum and colon.
2. To provide pilot data for the diagnostic accuracy of the LumenEye system for colitis severity, cancer, rectal polyps and benign disease of the rectum and anus

3 Participant Entry

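### Operators' views are collected only when they use the device, on a form with no acceptance item, so clinicians who stop early are under-represented and their decision to stop goes unrecorded

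*Combined protocol and SAP*

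**What the plan says.** Section 2.4 gives the primary outcome as "Both safety and patient and clinical acceptance of the LumenEye device with specialist consultation over the CHiP platform". Section 1.2 states the hypothesis at the level of the clinician: "The main hypothesis is that digital rectoscopy is safe and acceptable to clinicians including general practitioners".

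Section 2.3 describes two sources of clinician data.

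- **Operators.** "Clinicians will be asked to provide qualitative feedback data with each use concerning device performance". The questionnaire is "split into technical performance, views achieved, diagnostic yield, quality of the telemedicine interaction, patient outcome (discharged or referred to formal endoscopy) and adverse events".
- **Remote advisers.** "All clinicians providing advice and guidance via CHiP will be asked to provide data on the quality of the views, the stability of the platform", together with the diagnosis. No timing is given.

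On training, section 2.2 says "All clinicians performing investigations with the LumenEye will undergo training and quality assurance assessment", and also "The first 5 procedures will be performed with a proctor". It does not say whether the five are counted per clinician or per site. Neither the number of clinicians nor the number of examinations each will do is stated.

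Section 2.1 sets a target of 100 patients, and section 5 ends the study once the hundredth has been examined and had any further investigation needed. Section 6 describes a feasibility study analysed with univariate methods. It names no unit of analysis, no weighting by clinician and no acceptance threshold. The withdrawal criteria in section 3.4 concern patients only.

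**The concern.** The question is whether clinicians accept the device, but the unit of data collection is the examination. A clinician who decides against the device shows it by no longer using it, and under this plan that is also the moment their data end. The form they last completed did not ask whether they would continue, and nothing later asks why they stopped.

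The fixed total of 100 patients adds to this. Each examination that a reluctant clinician does not do is done by someone still using the device. If forms are pooled, a continuing user's form takes the place of the missing one.

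This is separate from the fact that repeated forms from one clinician are not independent. Allowing for clustering widens the interval but does not bring back an opinion that was never collected. What is at stake is one component of the primary outcome, and the reasons for stopping that a feasibility study is well placed to learn.

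**Working it through.** The plan has no acceptance figure to reproduce, and the target of 100 patients comes with no derivation. The check is therefore a reading of what is collected, followed by an illustration.

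**What is collected from whom (sections 2.2, 2.3 and 3.4)**

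| Clinician | Data under the plan | Acceptance or willingness to continue | Stopping and reason |
|---|---|---|---|
| Operator who continues | One form per examination | Not among the six domains | Not applicable |
| Operator who stops early | Few forms | Not among the six domains | Not collected |
| Trained, never starts (if any) | None | None | Not collected |
| CHiP adviser | Views, platform stability, diagnosis | Not listed | Not collected |

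**Illustration A.** None of these inputs is in the documents except the total of 100, taken here as one form per patient. Assume 10 trained clinicians whose chance of a favourable answer is 0.9 (4 clinicians), 0.7 (3) and 0.3 (3).

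- Per clinician, all trained: (4 × 0.9 + 3 × 0.7 + 3 × 0.3)/10 = 6.6/10 = 66%.
- Pooled per form: Σ(uses × rate)/Σ(uses).

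| Assumed use | Pooled calculation | Pooled | Excess over 66% |
|---|---|---|---|
| Even, 10 each | (40 × 0.9 + 30 × 0.7 + 30 × 0.3)/100 | 66% | 0 points |
| 16, 8 and 4 each, by keenness | (64 × 0.9 + 24 × 0.7 + 12 × 0.3)/100 | 78% | 12 points |
| 19 each (4), 7 each (3), 3 (1), none (2) | (76 × 0.9 + 21 × 0.7 + 3 × 0.3)/100 | 84% | 18 points |

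In the last row, averaging once per user instead of pooling gives (4 × 0.9 + 3 × 0.7 + 1 × 0.3)/8 = 6.0/8 = 75%. That is still 9 points above 66%, because the two who never started are absent.

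**Illustration B.** Assume six keen clinicians doing 15 examinations each at 90% favourable, and four reluctant ones doing 10 in all at 20%.

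- Pooled: (90 × 0.9 + 10 × 0.2)/100 = 83%.
- Per clinician: (6 × 0.9 + 4 × 0.2)/10 = 62%.
- Excess: 21 points.

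Across the two illustrations the excess runs from 0 to about 20 points. The whole range comes from the assumed link between volume of use and opinion, and the plan collects nothing that would locate the study within it.

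**Precision of a clinician-level figure.** At an assumed 10 clinicians, 6/10 accepting has an exact 95% interval of about 26% to 88%. If the five proctored procedures are per clinician and are done on study patients, at most 100/5 = 20 clinicians could complete them, so N is likely to be small.

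**The case against.** The strongest reply is that no bias has been shown. A reader might infer that acceptance is weighted towards the keenest users and is overstated. The documents do not support that. It needs forms pooled per use and volume that follows enthusiasm, and the plan states neither. Patients arrive through the IBD and GP routes in section 2.1, so volume could as easily follow patient flow or site. With even use the weighting excess is zero. This stands, and the size can only be given as a conditional range.

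A reader might also infer a group of trained clinicians who never start. Section 2.2 describes training for those who perform examinations and mentions no wider pool, so such a group is possible but not shown. Nor is it shown that a stopper would leave only one or two forms. If the proctored five are per clinician, anyone who completes them leaves about five. The point does not depend on either, because early stopping alone leaves the decision and its reason unrecorded.

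It would also be wrong to say that all clinician feedback depends on operating the device. The CHiP advisers are a separate source, and their view matters because the primary outcome includes specialist consultation. But they too are participants, and what they report does not cover whether a GP would adopt the device.

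Finally, the per-use form is about device performance, and for that purpose collecting it at each use is sensible. This is a fair defence of the form. It also confirms the gap, since neither source of clinician data contains a stated measure of acceptance. Feasibility status does not remove the point, because acceptance is part of this study's own primary outcome.

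**Conclusion.** The point holds as an unaddressed risk and a gap in measurement, not as a demonstrated bias. What rests on the text alone is this: operators are heard only through a per-use performance form without an acceptance item; the advisers' data do not fill the gap; and the plan contains no clinician-level survey, log of trained clinicians or record of stopping.

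Whether the resulting acceptance figure would be too high depends on pooling and on a link between use and opinion. Under the assumed scenarios the excess is 0 to about 20 points. Those figures rest on an invented number of clinicians, invented rates and invented volumes, and should be read only as showing that the effect could be nil or material. The plan should be changed because the study could not tell these cases apart and because the remedy is cheap.

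**What to change.** In section 2.3:

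1. Keep the per-use forms for technical performance.
2. Keep a log of every clinician trained, with role (GP or other) and number of uses.
3. Add one short end-of-study form for every trained clinician, including any who stopped or never started. It asks whether they would use the device in their practice and, if they stopped or did not start, why.

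In section 6:

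1. Report clinical acceptance as n/N of trained clinicians with an exact confidence interval, GPs separately.
2. Show non-responders as their own category.
3. Add a sensitivity analysis that counts non-responders who stopped as not accepting. This should not be the main rule, because clinicians may stop through redeployment, a lack of eligible patients or the study reaching its 100th patient.

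The cost is a log and one brief form per clinician, with no added burden on patients. The acceptance figure may come out lower, and its interval will be wide because clinicians are likely to be few.

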4.2.3 Contact details for reporting SAEs

Email: [contact]
Please send SAE forms to: [name], Department of Surgery and Cancer,
[name]
[name]

5 Assessment and Follow-up

We will record clinical outcome data in patients with a new diagnosis of IBD or colon cancer, and we will record if they underwent medical therapy, surgery or endoscopic therapy. The aim is to determine if the LumenEye improves the time to diagnosis and treatment, and ultimately outcome. The study will end when the 100th patient has been assessed and undergone any further investigation warranted by their presentation. Any incidental findings will be noted on the case report form and investigated as per the usual clinical pathways.

Data and all appropriate documentation will be stored for a minimum of 10 years after the completion of the study, including the follow-up period.

6 Statistics and data analysis

This is a feasibility study. The aim is to establish whether the device is acceptable and to establish the initial diagnostic performance of this device. This data will be used to form the basis of a power calculation for future studies. All data will be analysed using SPSS v. 20 and will be analysed using standard univariate statistical models.

7 Regulatory issues

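### The random post-cleaning swabs cannot by themselves confirm eradication of SARS-CoV-2, because nothing shows that a swabbed device carried virus before cleaning

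*Combined protocol and SAP*

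**What the plan says.** Section 2.3 (Analysis) sets a minimum number of swabs per device: "All LumenEye devices will undergo at least one random post-cleaning swab test for Covid-19". It gives the purpose in the same sentence: "to confirm the Tristel Trio cleaning system sufficiently eradicates SARS-COV-2 from the LumenEye". A bracketed sentence follows: "An analysis of this has been performed outside of the study which confirms the efficacy of the Tristel Trio system against SARS-COV-2". No data, method or reference is given for that analysis.

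Nothing in the document says how many devices will be used or swabbed, or what result would count as sufficient. It does not ask for a swab before cleaning or a positive control, and it does not link a swab to the Covid-19 status of the previous patient. Section 2.1 gives the number of patients ("The study aims to recruit 100 patients into the pilot study"), and Section 2.2 names three hospital trusts, with examinations done by primary care physicians. Neither gives a device count. Section 6 says only that data "will be analysed using standard univariate statistical models". Section 2.4 puts safety in the primary outcome but does not mention the swabs.

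**The concern.** A post-cleaning swab informs about cleaning only if there was virus to remove. Here the swab is taken at random, and the previous patient's status is neither required nor recorded. A run of negatives is therefore what one would see if cleaning works, and also what one would often see if cleaning fails but few devices were ever contaminated. The stated purpose treats the first explanation as the only one.

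What is at stake is one sentence in the eventual report. If the plan is followed as worded, a small number of negatives can be described as in-study confirmation of decontamination. The subject is not trivial: Section 1.1.4 makes a disposable manifold and this chemical clean the whole of reprocessing, and Section 4.1 counts Covid-19 transmitted during the procedure as an adverse event.

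**Working it through.** The plan gives no sample size, failure rate or confidence level for the swabs, so there is no figure of its own to reproduce. The check asks what an all-negative result could show.

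**Inputs**

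- Swabs per device: at least 1 (Section 2.3).
- Number of swabs, *k*: not stated. Assumed 3 to 20, taking one swab per device.
- Probability that a device carried virus before cleaning, *c*: not stated. Assumed 1% to 20%, with 100% as the case most favourable to the plan.
- Probability that cleaning fails on a contaminated device, *f*: not stated. 50% is used as a plainly unacceptable value.
- Swab sensitivity on the device surface, *s*: not stated. Assumed 100%, with 70% as a check.
- Swabs are taken as independent, with no false positives.

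**Step 1: what the swabs measure.** A swab is positive with probability *p* = *c* × *f* × *s*, and P(all *k* negative) = (1 − *cfs*)^*k*. Only the product enters, so the results cannot separate *c* from *f*. With 10 swabs and *s* = 1:

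- every device contaminated, cleaning fails 5% of the time: (1 − 1 × 0.05)^10 = 0.599
- 5% of devices contaminated, cleaning never works: (1 − 0.05 × 1)^10 = 0.599

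Ten negatives are equally probable under these two very different states.

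**Step 2: chance of an all-negative result when cleaning fails half the time** (*f* = 0.5, *s* = 1).

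| Prior contamination | 3 swabs | 10 swabs | 20 swabs |
|---|---|---|---|
| 1% | 0.995^3 = 0.985 | 0.995^10 = 0.951 | 0.995^20 = 0.905 |
| 5% | 0.975^3 = 0.927 | 0.975^10 = 0.776 | 0.975^20 = 0.603 |
| 10% | 0.95^3 = 0.857 | 0.95^10 = 0.599 | 0.95^20 = 0.358 |
| 20% | 0.90^3 = 0.729 | 0.90^10 = 0.349 | 0.90^20 = 0.122 |

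For 1% to 5% contamination and 3 to 10 swabs the range is 78% to 99%. A less sensitive swab raises every entry: at 5% contamination, 10 swabs and *s* = 0.7, (1 − 0.05 × 0.5 × 0.7)^10 = 0.9825^10 = 0.838.

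**Step 3: what zero positives would exclude.** The exact one-sided 95% upper limit on the swab-positive rate after 0/*k* is 1 − 0.05^(1/*k*):

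- *k* = 3: 63.2%
- *k* = 10: 25.9%
- *k* = 20: 13.9%

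These are limits on *p*. To turn one into a limit on *f*, divide by *cs*. With *c* = *s* = 1 the figures stand unchanged. With *c* = 20% and 10 swabs, 0.259/0.20 = 1.29, which exceeds 1, so not even complete cleaning failure is excluded.

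**Step 4: scale.** Excluding a failure rate of 10% with zero positives needs ln(0.05)/ln(1 − 0.10), rounded up to 29 swabs, if all devices were contaminated and the swab is perfect. With random swabs and 5% contamination it needs ln(0.05)/ln(1 − 0.005), rounded up to 598.

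**The case against.** Several points on the other side stand.

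The requirement is a minimum, so a site may take more swabs than one per device. But one is all that the plan guarantees, and Step 4 shows that extra random swabs help slowly when contamination is low.

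A reader might infer that the efficacy of the cleaning system is unsupported. The documents do not allow that. The same section cites an analysis done outside the study, and its content is not available here. The swabs can fairly be read as an in-use check added to that evidence. What remains is that the sentence about the swabs assigns the confirmation to them.

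A reader might also infer that negative swabs will be presented as proof on the primary safety outcome. No passage says so. The swabs are not a named endpoint, Section 6 gives no rule for them, and safety is also captured by adverse-event questions at each use and by four-weekly staff PCR tests.

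Nor is an all-negative result likely in every setting. With 20% contamination, 50% failure and 10 swabs it has probability 35%. With every device contaminated, 30% failure and 10 swabs it is 0.7^10, about 3%. The difficulty is that the plan does nothing to secure or document such favourable conditions.

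Finally, this is a 100-patient feasibility study and the swab is a hygiene check, which limits the weight of the point.

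**Conclusion.** The point holds in a limited form: these swabs, taken alone, cannot confirm that cleaning eradicates SARS-CoV-2 from the device. This rests on the design and on no assumed number, since a random swab with no evidence of prior contamination cannot distinguish successful cleaning from no exposure.

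The size does depend on assumptions. With a perfect swab and 50% cleaning failure, the all-negative probability runs from 78% to 99% (3 to 10 swabs, 1% to 5% contamination) down to 35% (10 swabs, 20% contamination). The upper limits of 63% and 26% after 0/3 and 0/10 are limits on the swab-positive rate. Reading them as limits on cleaning failure needs every device contaminated and a perfect swab.

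Nothing here suggests that the cleaning system fails or that the device is unsafe. It is a minor point about what may be concluded, and it is cheap to put right.

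**What to change.** Reword the sentence in Section 2.3 along these lines:

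*Every device will be swabbed after cleaning on one or more occasions, as an in-use spot check. Where a device has been used in a patient already known or suspected to have Covid-19, the swab will by preference follow that use, and the patient's status will be logged from available clinical information. We will report positives over swabs taken, by that status, with an exact one-sided 95% upper limit on the swab-positive rate. The efficacy of the cleaning system rests on the separate analysis.*

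Give a reference or short summary for the separate analysis, since the efficacy claim would then rest on it. State the number of devices.

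Cost: a weaker claim, a wording change and one log field, with no added swabs. Two limits remain. The plan describes no Covid-19 testing of patients, so status can come only from what is already known clinically, and there may be few or no exposed devices to swab. Patient status is also only a proxy for contamination of the device, so even negatives after such use should not be called confirmation. If the confirmatory claim is to be kept, the plan would need documented contamination before cleaning or a positive control, with a stated number of swabs; Step 4 of the working shows the scale.
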